1.3. Previous Experience with PulseRider Aneurysm Neck Reconstruction Device

1.3.1. Bench and Animal Studies

Bench and animal testing has been performed using the PulseRider Aneurysm Neck Reconstruction Device. Please refer to the Investigator Brochure for detailed summaries of the test protocols and corresponding reports.

1.3.2. PulseRider HDE Clinical Study

Pulsar Vascular Inc. sponsored a HDE clinical study to evaluate the safety and probable benefit of the PulseRider Aneurysm Neck Reconstruction Device under IDE G130268. The Adjunctive Neurovascular Support for Wide-Neck Aneurysm Embolization and Reconstruction Study (ANSWER) was a prospective, multi-center, non-randomized study designed to evaluate the safety of the PulseRider device in patients undergoing treatment for intracranial bifurcation aneurysms of the carotid terminus or basilar artery. Thirty-four subjects were enrolled in the clinical study at 10 clinical sites in the US.

The PulseRider is an adjunctive device to support the neck of the aneurysm and it is intended to be used with embolic coils. The device was placed at the neck of the intended target aneurysm and detached in 34/34 cases, a 100% success rate. The blinded core lab adjudicated Raymond I and II combined score was 87.9% at 180 days post-procedure. There were two secondary procedures performed during the course of the study. The HDE study was limited to basilar and carotid terminus aneurysms only and although the safety profile of the device is favorable and reported data is encouraging, a larger study in additional territories is desired.

A report of the full data set with six-month follow-up was submitted to the Food and Drug Administration (FDA) in June 2016. The HDE was approved on June 19, 2017 for use in bifurcation aneurysms in the carotid terminus and basilar arteries. Further detail on the ANSWER Study is located in the Investigator Brochure.

1.4. Rationale

The PulseRider is designed to allow for the treatment of wide-neck intracranial aneurysms at a bifurcation of the basilar artery, carotid terminus, MCA and ACOM. The PulseRider device, when used in combination with embolic agents, should enable endovascular treatment and occlusion of aneurysms that previously were untreatable or could only be treated with an open procedure. This potentially could result in higher rates of aneurysm occlusion, lower patient mortality and an acceptable rate of short-term and long-term morbidity.

1.5. Potential Risks and Benefits

1.5.1. Known Potential Risks

Risks that may be associated with the use of the PulseRider, the procedure, antiplatelet medications or general anesthesia are described in this section. Common risks (with anticipated frequency of < 20 %) include headache, dizziness, nausea and vomiting, groin injury or hemorrhage, pain at the insertion site, or insertion site hematoma/bleeding. All other risks are uncommon or rare and are expected to occur with frequency < 10% [Naggara et al. 2010].

Table 1.5.1A Anticipated Risks

Common risks with anticipated frequency of < 20%	
Dizziness	Insertion site hematoma/bleeding
Groin injury or hemorrhage	Nausea and vomiting
Headache	Pain at insertion site
Uncommon or rare risks with anticipated frequency of < 10%	
Adverse reaction to antiplatelet/anticoagulation agents	Hypertension
Adverse tissue reaction	Hypoesthesia
Allergic reaction and anaphylaxis from device and contrast media	Hypotension
Allergy to nickel	Hypothermia
Allergy to nitinol	Incomplete aneurysm occlusion
Aneurysm perforation or rupture	Increase in intracranial pressure
Aneurysm recanalization or regrowth	Infarction
Arteriovenous fistula	Infection including urinary tract infection
Blurry vision	Infection at insertion site
Cardiac arrhythmia	Intracerebral hemorrhage
Cardiac failure	Intracranial hemorrhage
Cerebral edema	Ischemia
Cerebral infarct	Laboratory abnormality
Coagulopathy	Mass Effect
Cognitive impairment	Myocardial infarction
Coil migration	Neurological deficits
Coil prolapse or herniation into normal vessel through or around device	Perforation
Coma	Perforator occlusion

Confusion	Phlebitis
Cortical blindness	Pneumonia
Cranial nerve deficit(s)	Post-procedure bleeding
Cranial nerve palsy	Pseudo-aneurysm formation
Death	Renal failure
Deep vein thrombosis	Retroperitoneal hematoma
Device delivery failure	Ruptured or perforated vessel or aneurysm
Device deployment difficulty	Seizure
Device fracture	Stenosis or occlusion within the device
Device migration	Stenosis or occlusion of parent vessel
Device misplacement	Stenosis or occlusion of perforator
Diplopia	Stenosis or occlusion of side branch
Dissection	Stenosis or occlusion of treated segment
Disseminated intravascular coagulation	Stroke
Ecchymosis	Thromboembolism
Edema	Tissue necrosis
Emboli (air, tissue, thrombotic and device)	Transient ischemic attack (TIA)
Emolic stroke	Vasospasm
Emergent neurosurgery	Vessel dissection
Facial numbness	Vessel occlusion
Fever	Vessel perforation
Fracture of delivery wire	Vessel thrombosis
Hematoma	Visual field deficit
Hemorrhage	Vision impairment
Hydrocephalus	Weakness left or right side

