The concept of using a neck bridge to support coils and to improve endovascular treatment for bifurcation aneurysms was first reported in 2001 with the initial introduction of the TriSpan device (Target Therapeutics/Boston Scientific, Fremont, CA) in Europe and Canada [Raymond 2001]. More recently physicians have been treating unruptured aneurysms using stents as adjunctive devices to support the coil mass. For bifurcation aneurysms, the Y-stent technique involves the passage of a second stent through the interstices of the first deployed stent. This technique is technically demanding and requires multiple steps, each with the possibility of technical complication [Fargen 2013, Spiotta 2011, Akgul 2011]. Y-stenting has become quite prevalent for wide neck aneurysms since endovascular therapy requires high packing density as there is a relationship between aneurysm volume, packing and compaction [Sluzewski 2004]. Dense packing aids in preventing recanalization of the lesion and SAH post-procedure. However, it has been noted, that over time, about 25% of cerebral aneurysms treated with embolic coils do show evidence of some refilling of the aneurysm sac [Slob 2005] which has furthered the need for new technology. Incomplete occlusion, incomplete packing, coil compaction, or coil migration into the intra-aneurysmal thrombus may contribute to recurrence and subsequent (re)bleeding [Henkes 2005].

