8.1.6. Unanticipated Adverse Device Effect (UADE)

Per 21 CFR 812.3(s), an unanticipated adverse device effect (UADE) is any serious adverse effect on health or safety or any life-threatening problem or death caused by, or associated with, a device, if that effect, problem, or death was not previously identified in nature, severity, or degree of incidence in the investigational plan or application (including a supplementary plan or application) or any other unanticipated serious problem associated with a device that relates to the rights, safety, or welfare of subjects.

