10.2. Sample Size Justification

Meta-analysis

As described above, a meta-analysis was executed to determine the safety Performance Goals for the proposed NAPA clinical study of the PulseRider using the R package ‘meta^a’ in a [R] environment, version 3.3-2. To obtain an overall proportion from studies reporting a single proportion, a random-effects model was chosen over a fixed-effect model to acknowledge the variations in study design. Additional characteristics of the methodology are:

- Inverse variance method used for weights
- DerSimonian-Laird method used to estimate τ^2
- Logit transformation
- Clopper-Pearson confidence interval for individual studies
- Continuity correction of 0.5 in studies with zero cell frequencies

Based on this meta-analysis, a rate of 9.9% rounded to 10% (95% CI: 5.9% - 16.1%) for death due to neurological causes or major ipsilateral stroke was calculated. A 5% margin of indifference for the primary safety endpoint is proposed, resulting in a PG of 15% for this endpoint. Based on the 1 year results of the ANSWER HDE Study, the anticipated rate for the primary safety endpoint is 7%. Results from a recently published meta-analysis [Fiorella 2017] of wide-neck bifurcation aneurysms indicate that the rate of complete occlusion at 1 year of wide-neck bifurcated aneurysms treated with conventional therapies is 46.3% (95% CI: 39.2% - 53.4%) whereas based on the ANSWER HDE Study the rate of complete occlusion is expected to be 58.8% with the PulseRider device. With Sponsor’s desire to seek superiority to a PG of 46.3% for the primary effectiveness endpoint and an expected attrition rate of 10%, one hundred sixty (160) subjects will provide 80% power for the primary safety endpoint and 85% power for the primary effectiveness endpoint.

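### Table 1.5.1A lists incomplete aneurysm occlusion as a risk below 10%, but the protocol's own planning rate implies about 41% without complete occlusion at 1 year

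*Combined protocol and SAP*

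**What the plan says.** Section 1.5.1 divides the anticipated risks into two groups. Six common ones are expected in fewer than 20% of subjects. For everything else: "All other risks are uncommon or rare and are expected to occur with frequency < 10" (per cent), with one outside review cited. The second block of Table 1.5.1A repeats the limit in its heading, "Uncommon or rare risks with anticipated frequency of < 10" (per cent), and lists both "Incomplete aneurysm occlusion" and "Aneurysm recanalization or regrowth". The table gives neither an occlusion standard nor a time point.

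Other sections give rates for the same or overlapping outcomes:

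- Section 10.2, planning rate for the 1-year effectiveness endpoint: "the rate of complete occlusion is expected to be 58.8% with the PulseRider device". The Protocol Summary uses the same figure.
- Section 1.3.2, earlier study of this device: "The blinded core lab adjudicated Raymond I and II combined score was 87.9% at 180 days post-procedure".
- Section 1.1, coiling in general: "about 25% of cerebral aneurysms treated with embolic coils do show evidence of some refilling of the aneurysm sac".

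Section 3.2.2 defines complete occlusion as Raymond class I. Class II is a residual neck and class III is residual filling of the sac. Section 3.2.3 treats classes I and II together as adequate occlusion.

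**The concern.** In the protocol's own vocabulary, an aneurysm that is not Raymond I is not completely occluded. A risk table that puts incomplete occlusion below 10% therefore implies a Raymond I rate above 90%, while the trial is sized on 58.8%. Both cannot describe the same expectation.

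Section 1.5.1 is the formal statement of known risks that investigators and IRBs read, and Sections 7.1 and 11.3.2 require risks to be discussed with patients before they consent. A reader who relies on the table alone would take the main way in which treatment can fall short to be uncommon, when the design expects it in about two subjects in five.

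**Working it through.** **Inputs.** Stated ceiling: 10% (Section 1.5.1, Table 1.5.1A). Planned complete occlusion: 58.8%; performance goal: 46.3%; 160 subjects, 10% attrition, stated effectiveness power 85% (Section 10.2). Raymond I and II combined at 180 days: 87.9%; 34 subjects enrolled; two secondary procedures (Section 1.3.2). Refilling after coiling: about 25% (Section 1.1).

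**Step 1. Is 58.8% really the working assumption?** Evaluable n = 160 × 0.9 = 144.

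- Standard error at the planning rate: √(0.588 × 0.412 / 144) = 0.0410.
- Wald power: Φ(0.125 / 0.0410 − 1.96) = 86.2%.
- With the null variance in the critical value: 85.6%.
- Exact binomial probability of passing the normal-approximation interval rule: 85.2%.

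All three agree with the stated 85%, so the trial is designed around 58.8%.

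**Step 2. Shortfall against Raymond I.** 100 − 58.8 = 41.2%, and 41.2 / 10 ≈ 4.1. This is about 59 of 144 or 66 of 160 subjects, where a 10% ceiling allows 14.4 of 144 or 16 of 160.

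**Step 3. Could small numbers in the earlier study explain it?** The percentage matches 20/34, so the shortfall would be 14/34. The count is inferred, not stated. The Clopper-Pearson 95% interval is 24.6% to 59.3%. If the true rate were 10%, the chance of 14 or more in 34 would be about 2 in a million. Chance does not explain it.

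**Step 4. Does the success rule agree with the table?** With 144 evaluable subjects, the smallest result whose lower 95% limit exceeds 46.3% is 79/144 = 54.9%. A successful trial could therefore have 65/144 = 45.1% endpoint failures. Those also include stenosis above 50% and retreatment, so this is an upper figure for incomplete occlusion alone.

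**Step 5. Narrower reading: residual sac filling only (Raymond III).** 100 − 87.9 = 12.1% at 180 days, which matches 4/33 (inferred). The 95% interval is 3.4% to 28.2%, and the chance of 4 or more in 33 at a true 10% is 0.42. This is nominally above 10% but statistically compatible with it.

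**Step 6. Recanalization or regrowth.** The only rate in the protocol for a comparable outcome is about 25% with some refilling after coiling. It is not specific to this device.

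**The case against.** The strongest reply is that the table never defines incomplete occlusion. If it means residual sac filling, the relevant device figure is 12.1% on about 33 subjects, which does not contradict a rate below 10%. The stated frequency also rests on an outside review whose definition and time point the documents do not give. This stands as a reason to define the term. It does not rescue the entry: the protocol reserves the word complete for Raymond I, and nothing in Section 1.5.1 signals a narrower sense.

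On recanalization, the 25% figure describes coils in general, over time, and appears as background on the problem that the device is meant to address. The earlier device study had two secondary procedures among 34 subjects (2/34 = 5.9%), which is below 10%. Secondary procedures are not the same as recanalization, but the conflict for this item is clearly weaker than for occlusion.

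Two larger consequences are tempting to infer.

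- **That the benchmark for unanticipated device effects is broken.** Section 8.1.6 does turn on effects "not previously identified in nature, severity, or degree of incidence in the investigational plan or application". But the part of that definition that uses incidence is confined to serious effects, life-threatening problems or death, whereas occlusion grade is mainly an imaging effectiveness outcome. The investigational plan is wider than this table and also contains the 58.8% and 25% figures. Section 8.1.5 judges its own category against the risk analysis report. A reference rate set too low would tend to over-call effects as unanticipated. Occlusion and retreatment are also endpoints in their own right, so an excess would be seen there.
- **That subjects are told too low a risk.** The example consent form is a separate document (Section 11.3.1) and its text was not available for this review, so this cannot be judged.

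A reader might also set the table against 100 − 46.3 = 53.7% and call the gap fivefold. Section 10.2 attributes 46.3% to conventional therapies. It is a performance goal, not an expected rate for this device.

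**Conclusion.** The contradiction over incomplete occlusion is real. Against a stated ceiling of 10%, the protocol's own planning rate implies 41.2% not completely occluded at 1 year, at least fourfold higher and above the 20% heading for common risks too. The entry for recanalization or regrowth is hard to reconcile with the background figure of about 25%, but that evidence is indirect.

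The conclusion rests on reading incomplete as not Raymond I, and on reading 58.8% as a complete occlusion rate, as the Protocol Summary and Section 10.2 do. Section 10.1.1 attaches the same 58.8% to adequate occlusion. On that label, 41.2% would fall short even of Raymond I and II combined, so the conflict would not be smaller. The confidence intervals rest on inferred counts; the 41.2% itself does not.

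This is a wrong stated frequency in the risk section. It does not affect the sample size, alpha, power or either decision rule, and both risks are at least disclosed by name.

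**What to change.** Remove incomplete occlusion and recanalization or regrowth from the block below 10% in Table 1.5.1A, and reword the sentence in Section 1.5.1 so that it no longer covers every remaining risk. State the two items separately, each with its definition, time point and source:

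- not Raymond I at 1 year: about 41% (planning rate, Section 10.2);
- Raymond III at 180 days: about 12% (earlier device study, Section 1.3.2), noting the small sample and that it is compatible with 10%;
- some refilling over time: about 25% (coiled aneurysms in general, Section 1.1), labelled as not specific to this device.

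Then check the consent template against the corrected table. Leave Section 8.1.6 as it is, because it restates a regulation and trial figures do not belong in it.

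The cost is two table rows, one sentence and a consistency check. The downside is a less favourable stated risk.

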1.5.2. Minimization of Risk

Efforts will be made to minimize the potential risks through the following:

1. Investigators who participate in the study will be experienced and skilled in neuro-intervention surgery and will have adequate resources to conduct the clinical study.
2. The study has been designed to ensure treatment and follow-up of subjects are consistent with current medical practice.
3. Each investigator will ensure oversight and approval of the study by the IRB prior to initiation of the study at the investigation site.
4. The investigator and study personnel will be trained on the study protocol.
5. The investigators and appropriate personnel will undergo training on the use of the PulseRider device prior to first use during the study.
6. Subjects will be carefully evaluated against the inclusion/exclusion criteria prior to being enrolled in the study to ensure that their diagnosis and medical status are appropriate for participation.
7. Subject status will be monitored by the investigator or designee throughout the follow-up period as defined in the study protocol.

8. The investigator or designee will evaluate the subject for any adverse events potentially related to the procedure or to the device. Device status will also be assessed using appropriate imaging modalities defined in the study protocol.
9. All reportable adverse events for the study will be reviewed and adjudicated by a CEC.
10. Data from all investigation sites will be monitored throughout the study to evaluate protocol compliance and identify any issues that may affect the safety and welfare of the subjects.
11. De-identified angiograms will be reviewed by an independent core laboratory to assess PulseRider device placement and occlusion of the aneurysm. Sites are requested to provide de-identified images to the core lab. In the event, images are received with any patient identifiers, the core lab's proprietary software removes all patient protected health information (PHI) as images are processed through their system. Each image is then reviewed by a radiology technician to ensure that all PHI was adequately removed. This two-fold process is completed before image exam is uploaded and reviewed. The radiology technician/assessor will also be blinded to the subject's previous medical history.

1.5.3. Known Potential Benefits

The potential benefits of the PulseRider device are that it may decrease or stop the blood flow into the aneurysm and thus decrease or eliminate the symptoms that the aneurysm is causing (if any) or decrease or eliminate the chance of future aneurysm rupture which often leads to stroke or death. The specific benefits of the device include that it may be a safer and faster procedure than currently used methods to treat bifurcation aneurysms and it may be possible to treat patients whose aneurysms previously could not be treated or have been incompletely treated with other techniques (e.g. previously placed coils). By changing the flow in the blood vessel and aneurysm, it is hoped that the PulseRider device will lead to a more lasting cure of the aneurysm. Although there may be no direct benefits of study participation, subject participants will undergo an enhanced level of clinical scrutiny compared to routine clinical care, which may provide some indirect health benefits. The potential benefits of the device outweigh the anticipated risks.

2. Objectives and Purpose

2.1. Objectives

The primary objective of this study is to determine the safety and efficacy of the PulseRider as an adjunctive therapy in conjunction with coil embolization in the minimally invasive endovascular treatment of intracranial aneurysms at a bifurcation of the basilar artery, carotid terminus, MCA, and ACOM. The data will be generated under an IDE and will be used to support a Pre-market Approval Application.

3. Study Design and Endpoints

3.1. Description of the Study Design

This study is designed as a prospective, multi-center, single-arm investigation of the PulseRider Aneurysm Neck Reconstruction Device used in conjunction with coil embolization in the treatment of unruptured wide-neck bifurcation intracranial aneurysms of the basilar artery, carotid terminus, MCA and ACOM. Up to 160 evaluable subjects will be enrolled at up to 28 clinical sites throughout the United States.

For this study, a single-arm design is deemed appropriate as there are currently no approved comparator devices indicated for the treatment of wide-neck bifurcation aneurysms available in the US. Subjects with unruptured, angiographically confirmed wide-neck (\geq 4 mm or a dome-to-neck ratio < 2) intracranial aneurysms located at the bifurcation of the basilar artery, carotid terminus, MCA and ACOM arising from the parent vessel for the target aneurysm with a diameter of 2.0 mm to 4.5 mm will be enrolled and expected to be followed through five year post-procedure.

3.2. Study Endpoints

3.2.1. Primary Endpoint - Safety

Composite of Neurological Death or Major Ipsilateral Stroke (in downstream territory) up to 1 year post-procedure:

Stroke is defined as rapidly developing clinical signs of focal (or global) disturbance of cerebral function lasting more than 24 hours with no apparent cause other than of vascular origin, including ischemic stroke and/or hemorrhagic stroke (i.e., intraparenchymal hemorrhage (IPH), subarachnoid hemorrhage (SAH), subdural hemorrhage (SDH), epidural hemorrhage (EDH)) [Hatano 1976].

Major Stroke is defined as stroke with symptoms persisting for more than 24 hours AND a sudden increase in the NIHSS of the subject by > 4 .

Minor Stroke is defined as stroke with symptoms persisting for more than 24 hours and a sudden increase in the NIHSS of the subject by 1-3.

TIA is defined as stroke symptoms resolving within ≤ 24 hours.

This endpoint will be adjudicated by the independent Clinical Events Committee (CEC).

[figure not shown]

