Sample Size:	A total of 160 subjects will be enrolled into the study.
Number of Sites:	Up to 28 clinical sites in the US
Study Population:	Subjects with unruptured, angiographically confirmed wide-neck (\geq 4 mm or a dome-to-neck ratio $<$ 2) intracranial aneurysms located at the bifurcation of the basilar artery, carotid terminus, MCA and ACOM arising from the parent vessel for the target aneurysm with a diameter of 2.0 mm to 4.5 mm will be eligible for the study.

Study Procedures:

The study evaluation time points include:

1. Screening/Baseline
2. Procedure
3. Hospital Discharge
4. 30 Day Follow-up (Clinic Visit)
5. 180 Day Follow-up (Clinic Visit)
6. 1 Year Follow-up (Clinic Visit and DSA)
7. 2 Year Follow-up (Telephone Call)
8. 3 Year Follow-up (Clinic Visit and DSA or MRA)
9. 4 Year Follow-up (Telephone Call)
10. 5 Year Follow-up (Clinic Visit and DSA or MRA)

Primary Safety Endpoint:

Composite of Neurological Death or Major Ipsilateral Stroke (in downstream territory) up to 1 year post-procedure:

- *Stroke is defined as rapidly developing clinical signs of focal (or global) disturbance of cerebral function lasting more than 24 hours with no apparent cause other than of vascular origin, including ischemic stroke and/or hemorrhagic stroke (i.e., intraparenchymal hemorrhage (IPH), subarachnoid hemorrhage (SAH), subdural hemorrhage (SDH), epidural hemorrhage (EDH)). [Hatano 1976].*
- *Major Stroke is defined as stroke with symptoms persisting for more than 24 hours AND a sudden increase in the NIHSS of the subject by ≥ 4 .*

Primary Effectiveness Endpoint:

Complete Occlusion:

Rate of complete aneurysm occlusion (Raymond I) without significant parent artery stenosis ($> 50\%$ stenosis) or prior retreatment at 1 year post-procedure.

Secondary Effectiveness Endpoints:

- Technical Success is defined as successful implantation of device— physician able to access target aneurysm, deploy PulseRider® device at the neck of aneurysm and device was detached successfully
- Ability to retain embolic coils within aneurysm immediately post-procedure (as evaluated by the core lab)
- Complete aneurysm occlusion at 3 years and 5 years
- Adequate aneurysm occlusion (defined as Raymond I and II combined) at 1 year, 3 years and 5 years

- The percentage of target aneurysms that are retreated through 1 year, 3 years and 5 years
- The percentage of subjects with significant stenosis defined as $> 50\%$ at implant site at 1 year, 3 years and 5 years.

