The composite safety endpoint applied by Fiorella et al. is reasonably dissimilar to the NAPA IDE primary safety endpoint of major ipsilateral stroke or death due to neurological causes at 1 year post-procedure. As a result, the NAPA IDE performance goals for safety was determined from a systematic review of literature published in OVID and PubMed between January 1, 2012 and April 25, 2017. After de-duplication, a full text search in QUOSA was performed limiting results to WNBA located at NAPA IDE aneurysm locations. The following inclusion/ criteria were applied, yielding 7 unique articles for safety with Forest Plot shown in Figure 10.1.1A. [Brassel 2015, Fields 2011, Labeyrie 2017, Pierot 2015, Peirot 2015 Sivan-Hoffman 2015, Zhao 2012].

Included articles:

- Article reporting clinical performance and safety results on equivalent comparator(s) [WEB, pCONUS, BARREL, X/Y stenting]
- Wide neck or complex bifurcation aneurysms found at MCA, ACOM, Basilar tip, carotid terminus with at least 80% or more unruptured aneurysms and where ≥ 5 patients were included in a series
- Clinical follow-up between 10 and 14 months;

[figure not shown]
Excluded articles:

- Technical or reviews (systematic and none) with non-extractable data by treatment modality

- No clinical performance and safety results on target device(s) and/or equivalent comparator(s)
- Use of the target device(s) and/or equivalent comparator(s) was not the main focus of the study
- Studies where the subject device was used in patients, but no safety or performance outcomes were reported
- Abstract, report, or article could not be retrieved
- Duplicate or non-English articles language

Of the included articles, all reported safety events were evaluated and neurological deficits that resulted in a sudden change in NIHSS of 4 or more (when reported) or as determined by a Codman neurosurgeon to cause a change in NIHSS of 4 or more were deemed to meet the primary safety endpoint. Based on this meta-analysis, a rate of 9.9% rounded to 10% (95% CI: 5.9% - 16.1%) for death due to neurological causes or major ipsilateral stroke was identified. A 5% margin of indifference for the primary safety endpoint is proposed, resulting in a Performance Goal (PG) of 15% for this endpoint.

Figure 10.1.1A Forest Plot: Seven References with Usable Data to Estimate the Anticipated Primary Safety Endpoint at 12 Months

Primary Safety Endpoint Hypotheses:

Null Hypothesis H_0 : $p_{\text{Major Stroke/Death}} \geq 15\%$

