Alternative hypothesis H_A : $p_{\text{Major Stroke/Death}} < 15\%$

Where $p_{\text{Major Stroke/Death}}$ is the rate of Composite of Neurological Death or Major Ipsilateral Stroke (in downstream territory) up to 1 year post-procedure.

Decision Criterion: The decision will be made to reject the null hypotheses and conclude the alternative hypothesis if the upper bound of a two-sided 95% normal approximation based confidence interval is < 15%.

Primary Effectiveness Endpoint Hypotheses:

Null hypothesis H_0 : $p_{\text{CompleteOcclusion}} \leq 46.34\%$

Alternative hypothesis H_A : $p_{\text{CompleteOcclusion}} > 46.3\%$

Where $p_{\text{CompleteOcclusion}}$ is the rate of complete aneurysm occlusion without significant parent artery stenosis ($> 50\%$ stenosis) or prior retreatment at 1 year post-procedure.

Decision Criterion: The decision will be made to reject the null hypotheses and conclude the alternative hypothesis if the lower bound of a two-sided 95% normal approximation based confidence interval is $> 46.3\%$.

Study Success:

The study will be deemed to be a success if the primary safety and effectiveness endpoint null hypotheses are both rejected.

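### Major stroke, a component of the primary safety endpoint, is an NIHSS rise of 4 or more in the Protocol Summary but more than 4 in section 3.2.1, where a rise of exactly 4 has no class

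*Combined protocol and SAP*

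**What the plan says.** The primary safety endpoint is neurological death or major ipsilateral stroke up to 1 year. Four places bear on how large an NIHSS rise makes a stroke major:

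- **Protocol Summary, Primary Safety Endpoint:** symptoms beyond 24 hours "AND a sudden increase in the NIHSS of the subject by ≥ 4".
- **Section 3.2.1, major stroke:** the same sentence, but "AND a sudden increase in the NIHSS of the subject by > 4".
- **Section 3.2.1, minor stroke:** "a sudden increase in the NIHSS of the subject by 1-3".
- **Section 10.1.1, source of the performance goal:** the literature review counted "neurological deficits that resulted in a sudden change in NIHSS of 4 or more" where the score was reported, and otherwise relied on a neurosurgeon's judgement against the same threshold.

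Section 3.2.1 also says that the independent CEC adjudicates this endpoint. The hypotheses in section 10.1.1 and the analysis in section 10.3.4 refer to major ipsilateral stroke without restating a threshold. Section 10.4 tells the CEC to apply the criteria that the protocol specifies, which leads back to the conflicting text.

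**The concern.** The threshold decides which strokes enter the numerator of a primary endpoint, and the study succeeds only if that endpoint's null hypothesis is rejected. The two definitions disagree at a rise of exactly 4 points. Section 3.2.1 is also incomplete in itself: the NIHSS takes whole-number values, so classes of 1-3 and more than 4 leave a hole at 4.

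The error has a direction. Every rise above 4 is also a rise of 4 or more, so following section 3.2.1 can only lower the trial's count. The 15% goal was derived with the wider threshold. This is a single-arm study judged against a fixed goal, so no control group is affected in the same way and nothing offsets the mismatch. If the conflict is found only when a 4-point stroke reaches adjudication, the threshold of a primary endpoint would be chosen with data in hand.

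**Working it through.** **Step 1. Classify a stroke lasting more than 24 hours with a rise of exactly 4.**

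| Source | Class of a 4-point stroke |
|---|---|
| Protocol Summary (≥ 4) | Major; an endpoint event if ipsilateral in the downstream territory |
| Section 3.2.1, major (> 4) | Not major |
| Section 3.2.1, minor (1-3) | Not minor |
| Section 10.1.1, literature events (4 or more) | Counted |

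Three of the four statements fit a threshold of ≥ 4. Only the major-stroke line in section 3.2.1 does not.

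**Step 2. Find how many events the safety criterion tolerates.**

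Inputs: goal 15% (pooled 9.9%, rounded to 10%, plus a 5-point margin; section 10.1.1). The null hypothesis is rejected "if the upper bound of a two-sided 95% normal approximation based confidence interval is < 15"% (section 10.1.1). 160 subjects are enrolled with 10% attrition (section 10.2), so 160 × 0.9 = 144.

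Upper bound = p + 1.96 × √(p(1 − p)/n), with p = x/n:

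- 14/144: 0.0972 + 1.96 × 0.0247 = 14.56%, passes.
- 15/144: 0.1042 + 1.96 × 0.0255 = 15.41%, fails.
- 16/160: 0.1000 + 1.96 × 0.0237 = 14.65%, passes.
- 17/160: 0.1063 + 1.96 × 0.0244 = 15.40%, fails.

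At the boundary, the class given to a single 4-point stroke reverses the result.

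**Step 3. Chance of passing when the device does not meet the goal.**

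Let f be the share of qualifying events that are non-fatal strokes of exactly 4 points. The documents give no value for f, so the values below are assumptions. If the true rate under ≥ 4 is 15%, section 3.2.1 counts a rate of 0.15 × (1 − f). The chance of passing is the binomial probability of at most 14 events in 144, or at most 16 in 160. The last column uses an exact (Clopper-Pearson) upper bound, which allows at most 13 events in 144.

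| f | Rate counted under > 4 | Stated interval, n = 144 | Stated interval, n = 160 | Exact bound, n = 144 |
|---|---|---|---|---|
| 0 | 15.0% | 4.3% | 4.3% | 2.4% |
| 5% | 14.25% | 7.1% | 7.2% | 4.1% |
| 10% | 13.5% | 11.1% | 11.6% | 6.8% |
| 20% | 12.0% | 24.3% | 26.1% | 16.6% |

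**Step 4. The same calculation at the planned rate.**

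Section 10.2 anticipates 7%. With 144 subjects and at most 14 events, the chance of passing is 92.0% at f = 0, 96.1% at f = 10% (rate 6.3%) and 98.5% at f = 20% (rate 5.6%). The expected number of reclassified events is 144 × 0.07 × f: about 1 at f = 10% and about 2 at f = 20%.

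**The case against.** The strongest objection is that the finding rests on one symbol in text extracted from a PDF. A ≥ printed as an underlined > could lose its underline, and the 1-3 minor class beside it fits only ≥ 4. That is possible but not shown: the ≤ in the transient ischaemic attack definition of the same section survived extraction, as did ≥ in the Protocol Summary. The source PDF should be checked.

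It can also be said that this is a clerical slip and that nobody chose > 4. That is probably so, and it makes the correction obvious. It does not tell a committee reading section 3.2.1 what to do with a 4-point stroke.

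The points about size largely stand:

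- No value of f is supported by the documents. Neurological deaths count whatever the threshold, which limits f.
- A true rate of 15% is the case least favourable to the plan. At 7% the effect is small.
- The analysis in section 10.3.4 covers the modified intent-to-treat set with multiple imputation, so the complete-case figures at 144 are an approximation. The figures at 160 are close to them.
- The goal is not a clean measurement of events at 4 or more, because NIHSS was not always reported and a margin was added. The direction of the mismatch is secure; its exact size is not.

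Finally, the CEC charter may already settle the threshold. It is not among the documents, and section 10.4 sends the committee to the protocol's own criteria.

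**Conclusion.** The concern holds: section 3.2.1 is wrong as written. It contradicts the Protocol Summary, leaves a rise of exactly 4 unclassified and does not match the events behind the performance goal. No other section resolves this.

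The classification conflict follows from the text alone. The size depends on f. At a true rate of 15% and f between 5% and 20%, the false-success probability is 7.1% to 24.3%, against 4.3% with the consistent definition (n = 144, stated interval). Near the planned 7% rate, about one or two events would be reclassified at f of 10% to 20%, and the conclusion would seldom change. The bias arises only if > 4 is the threshold actually applied. It must be corrected because it concerns the event definition of a primary endpoint on which study success depends, and any error can go only in the device's favour.

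**What to change.** Confirm the symbol in the source PDF. If it reads > 4, change the major-stroke definition in section 3.2.1 to an NIHSS increase of ≥ 4. This agrees with the Protocol Summary, closes the gap above the 1-3 minor class and matches the literature events in section 10.1.1. State the same threshold in the CEC charter and the separate SAP. If any stroke with a rise of exactly 4 has already been adjudicated, review its classification under the corrected definition.

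The cost is one symbol in the protocol and a check of the charter. Sample size, visits and procedures are unchanged.
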